CLINICAL TRIAL PROTOCOL

Investigational Product:
UBITh[®] CGRP Immunotherapy (UB-313)

A Phase 1 Randomized, Double-Blind, Placebo-Controlled, First-in-Human
Study to Evaluate the Safety, Tolerability, and Immunogenicity of UBITh[®]
CGRP Immunotherapy (UB-313) in Healthy Participants

EudraCT: 2022-000798-19

Protocol Number:
UB-313-101

Final Version 3.0
Date: 13 APRIL 2023

This document contains confidential information and is the property of Vaxxinity Ltd. (Vaxxinity, further referred to as the Sponsor). The receiver(s) of this document understand(s) and agree(s) that this document is not to be disclosed to any unauthorized third party without prior written agreement issued by the Sponsor. The need to disclose certain information contained in this document for the purpose of obtaining informed consent from potential participants or their legally acceptable representative(s) will be considered as exceptions.

SYNOPSIS

Protocol Number	UB-313-101
Title of Study	A Phase 1 Randomized, Double-Blind, Placebo--Controlled, First-in-Human Study to Evaluate the Safety, Tolerability, and Immunogenicity of UBITh® CGRP Immunotherapy (UB-313) in Healthy Adults
Study Site	This study will be conducted at one study center (Center for Clinical Pharmacology) in Leuven, Belgium
Development Phase	Phase 1, First-in-human
Study Objectives	
Primary Objectives:
 
 • To evaluate the safety and tolerability of UB-313, when administered at selected dose regimens given intramuscularly (IM) to healthy adults. • To evaluate the anti-calcitonin gene-related peptide (anti-CGRP) specific antibody responses to selected UB-313 dose regimens in healthy adults. 
Secondary Objective:
 
 • To evaluate the effects of selected UB-313 dose regimens on capsaicin-induced dermal blood flow (DBF) as a surrogate marker of target engagement. 
Exploratory Objectives:
 
 • To evaluate the effects of selected UB-313 dose regimens on CGRP concentrations in serum. • To characterize antibodies generated by UB-313. • To examine cytokine release induced by UB-313.
Endpoints	
Primary Endpoints
 
Safety will be assessed by adverse events (AEs), adverse events of special interest (AESIs), medically attended adverse events (MAAEs), local (injection site) and systemic (generalized) reactions (i.e., reactogenicity), clinical laboratory assessments (e.g., chemistry, hematology, urinalysis), vital signs, neurological and physical examinations, and electrocardiograms (ECGs) through the end of study.
 
Immunogenicity will be measured by serum anti-CGRP antibody titers and analyzed from baseline to Week 16 and through the end of study (Week 44).
 
Secondary Outcome Measure/Endpoints
 
Pharmacodynamics (PD) of the immune response will be measured by the inhibition of capsaicin-induced increase in DBF and analyzed from baseline to Week 16 and either until return to baseline or until Week 44, whichever comes first.
 
Exploratory Outcome Measures/Endpoints
 
Exploratory outcome measures may include but are not limited to the following:
 
 • CGRP concentrations in serum through the end of study. • Antibody titers against components of UB-313 (i.e., CpG1 and UBITh1) through the end of study. • Isotype-specific anti-CGRP antibody titers through the end of study. • Cytokine release from peripheral blood mononuclear cells stimulated with a component of UB-313 (T-cell ELISpot) through Week 16.

Methodology	
This single center, double-blind, placebo-controlled, multidose regimen, first-in-human (FIH) study of UB-313, an anti-CGRP peptide -based immunotherapeutic candidate, is designed to assess the safety, tolerability, and immunogenicity of 4 selected UB-313 dose regimens in healthy adults.
																																										
	
Screening Period
																																										
	
All participants will undergo Laser Speckle Contrast Imaging (LSCI) assessments at Screening to ensure a capsaicin response of at least 100% increase in DBF.
																																										
	
Following Screening, all eligible participants (approximately 40) will be randomized to receive 3 IM injections of UB-313 or placebo in a staggered manner by cohort as described below.
																																										
	
Investigational Product Dosage and Schedule:
																																										

Cohort
 
1 (N=10)
 
2 (N=10)
 
3 (N=10)
 
4 (N=10)
	
  
 Cohort	Number of Participants	Dose Regimen (0.5mL)	
 
 		Week 1	Week 4	Week 12	
   
 1 (N=10)	8	100 µg	100 µg	100 µg	
 
 Placebo	Placebo	Placebo	
 
 2 (N=10)	8	300 µg	100 µg	100 µg	
 
 Placebo	Placebo	Placebo	
 
 3 (N=10)	8	300 µg	300 µg	300 µg	
 
 Placebo	Placebo	Placebo	
 
 4 (N=10)	8	600 µg	100 µg	100 µg	
 
 Placebo	Placebo	Placebo	
  
	Cohort	Number of Participants	Dose Regimen (0.5mL)					Week 1	Week 4	Week 12	1 (N=10)	8	100 µg	100 µg	100 µg	Placebo	Placebo	Placebo	2 (N=10)	8	300 µg	100 µg	100 µg	Placebo	Placebo	Placebo	3 (N=10)	8	300 µg	300 µg	300 µg	Placebo	Placebo	Placebo	4 (N=10)	8	600 µg	100 µg	100 µg	Placebo	Placebo	Placebo
Cohort	Number of Participants	Dose Regimen (0.5mL)																																									
		Week 1	Week 4	Week 12																																							
1 (N=10)	8	100 µg	100 µg	100 µg																																							
		Placebo	Placebo	Placebo																																							
2 (N=10)	8	300 µg	100 µg	100 µg																																							
		Placebo	Placebo	Placebo																																							
3 (N=10)	8	300 µg	300 µg	300 µg																																							
		Placebo	Placebo	Placebo																																							
4 (N=10)	8	600 µg	100 µg	100 µg																																							
		Placebo	Placebo	Placebo																																							
	
Double-Blind Period
																																										
	
Eligible healthy participants will be enrolled into 1 of the 4 cohorts, as previously described. For safety purposes, dosing of all cohorts will be staggered. Sentinel dosing will be performed in Cohorts 1 (first dose of 100 µg), 2 (first dose of 300 µg), and 4 (first dose of 600 µg). The remaining participants in a cohort may be enrolled following a safety review conducted at least 24-hours after sentinel dosing; however, no more than 4 participants will be dosed within a 24-hour period.
																																										
	
Once all escalation safety evaluable participants within each of the dose levels (100 µg for Cohort 1, and 300 µg in Cohorts 2 and 3) have been observed for 1 week following their first dose of study Investigational Medicinal Product (IMP), all available safety data will be reviewed by the Safety Review Committee (SRC) before progressing to the next higher dose cohort (100 µg to 300 µg to 600 µg).
																																										

	
Cohort 3 may begin dosing at least 24 hours after all participants in Cohort 2 have received their first dose, and available (blinded) safety and tolerability data have been reviewed by the SRC. Based on the available data, a decision will be made to begin dosing of Cohort 3.
 
Participants will be provided with a diary. Starting the day of IMP administration, they will fill in the diary daily for 7 days, recording their temperature, and any solicited local and systemic symptoms of reactogenicity.
 
Capsaicin Challenge
 
A capsaicin-induced increase in DBF model will be used to assess the PDs of the UB-313-mediated immune response. Personnel who will perform these assessments will not be involved in UB-313 safety and tolerability evaluation due to the potential of unblinding. The capsaicin challenge will be conducted at Screening, Baseline before the first dose, and every 4 weeks up to Week 20 and subsequently every 8 weeks until the end of study at Week 44. After Week 16, LSCI assessment may no longer be required once the average capsaicin induced DBF increase within that cohort has returned to baseline (i.e., DBF response ± 2 SD before administration of IMP within a cohort).

Total Expected Number of Participants	Approximately 40 eligible healthy male and female participants (10 per cohort) will be enrolled to receive UB-313 or placebo.
Main Inclusion Criteria	
Full details of inclusion criteria are listed in the protocol. The main inclusion criteria include:
 
• Is a male or female aged 18 to 55 years old, inclusive, at time of informed consent.• Has a body mass index between 18 and 30 kg/m², inclusive at Screening, and with a minimum weight of 50 kg.• Male participants and their partners of childbearing potential must commit to the use of highly effective contraceptives for the study duration and for at least 12 weeks after the last dose. Men must refrain from donating sperm during this same period.• Female participants must be of nonchildbearing potential, or, for women of childbearing potential, must be willing to practice highly effective contraception throughout the duration of the study and for at least 24 weeks following the last dose.
Main Exclusion Criteria	
Full details of exclusion criteria are listed in the protocol. The main exclusion criteria include:
 
• Has a history of clinically significant medical or psychiatric conditions, which in the opinion of the Investigator may compromise the participant's safety or the scientific value of the study, posing an unacceptable risk to the participant or interfere with the participant's ability to comply with study procedures or abide by study restrictions.• Presents any concern by the Investigator regarding safe participation in the study or for any other reason (including contraindication to MRI) that the Investigator considers the participant inappropriate for participation in the study.• Has a recent history (within the past year of Screening) of migraine headache.• Has unsuitable skin characteristics for the dermal capsaicin challenge as determined by the Investigator.

	
Has not demonstrated at least a 100% increase in DBF following capsaicin challenge as part of Screening procedures and measured through LSCI.
Investigational Medicinal Product	
UB-313 drug product is a synthetic CGRP peptide-based immunotherapy formulated in CpG1 and Adju-Phos®. It is provided in single dose vial (peptide: 100 µg, 300 µg, or 600 µg; dosage volume: 0.5 mL).
 
Placebo is 0.9% sodium chloride (normal saline), preservative free for injection.
 
IMP will be either UB-313 or placebo and can also be referred to as study drug.

Participation Duration	
The total study participation will last up to 48 weeks, including:
 
Screening period: up to 4 weeks
 
Double-blind period: 44 weeks

Statistical Considerations	
As this is an FIH study, the sample size is based on the exploratory nature of the design. No statistical power to be considered to determine the sample size.
 
Primary time-points for immunogenicity and PD are two-fold:
 
a) First phase at the end of Week 16 for evaluating maximal immuno-responses elicited by the 4 dosage regimens (i.e., cohorts) of UB-313
 
b) Second phase of response maintenance period after Week 16 until the end of study (Week 44), in which effects of the 4 dosage regimens of UB-313 on the duration of responses will be evaluated.
 
When any cohort completes Week 16, first phase analyses can be conducted based on cleaned cohort data up to Week 16. To maintain blinding for the remainder of the study, the first phase analyses will be conducted and reviewed only by a designated and independent team before the end of study final database lock. The purpose of the early analyses of first phase data prior to the completion of the study is to have an early read out of the first part of the primary immunogenicity and PD results to refine the development plan. Design of the second phase of the study will not be changed based on results from the first phase data.

Table 1: Study Schedule of Assessments

The Investigator may perform visits outside of the scheduled study visits (unscheduled visits) listed in the Schedule of Assessments table to conduct evaluations or assessments required to protect the well-being of the participant.

Visit Number ¹	Screen ²	V1 ^{2,5}		V1a ⁵	V1b ⁵	V2	V3 ⁵		V3a ⁵	V3b ⁵	V4	V5	V6 ⁵		V6a ⁵	V6b ⁵	V7	V8	V9, V10, V11	V12/ET
Week	Up to 4 wks	W0				W1	W4				W5	W8	W12				W13	W16	W20, W28, W36	W44
Day (Visit Window)	-28 to -1	D1 (-3D)	D1 --	D2	D3	D8 ($\pm 3D$)	D29 (-3D)	D29 ($\pm 3D$)	D30	D31	D36 ($\pm 3D$)	D57 ($\pm 5D$)	D85 (-3D)	D85 ($\pm 3D$)	D86	D87	D92 ($\pm 3D$)	D113 ($\pm 7D$)	D141, D197, D253 ($\pm 14D$)	D309 ($\pm 14D$)
Visit Type	SRN	Pre IMP	IMP	CRU	TC	CRU	Pre IMP	IMP	CRU	TC	CRU	CRU	Pre IMP	IMP	CRU	TC	CRU	EoT CRU	CRU	EoS/ET CRU
General Assessments and Procedures																				
Informed consent	X																			
Demographic	X																			
Medical history	X																			
Eligibility assessment	X	X																		
Medication review	X	X	X	X	X	X	X	X	X	X	X	X	X	X	X	X	X	X	X	
AE/SAE review ³	X	X	X	X	X	X	X	X	X	X	X	X	X	X	X	X	X	X	X	
Investigational Medicinal Product Administration and Assessments																				
Randomization		X																		
IMP Injection ¹⁸			X					X								X				
Solicited local and systemic reactions assessment			X					X							X					
Extended unit stay ⁵			X ⁵					X							X					
Diary review ¹⁰			X	X		X		X	X		X				X	X		X		
General Safety Assessments																				
Vital signs (pre- and post-IMP) ^{6,7}	X		X	X		X		X	X		X	X		X	X		X	X	X	X
Height	X																			

Visit Number ¹	Screen ²	V1 ^{2,5}		V1a ⁵	V1b ⁵	V2	V3 ⁵		V3a ⁵	V3b ⁵	V4	V5	V6 ⁵		V6a ⁵	V6b ⁵	V7	V8	V9, V10, V11	V12/ET
Week	Up to 4 wks	W0				W1	W4				W5	W8	W12				W13	W16	W20, W28, W36	W44
Day (Visit Window)	-28 to - 1	D1 (-3D)	D1 --	D2	D3	D8 (±3D)	D29 (-3D)	D29 (±3D)	D30	D31	D36 (±3D)	D57 (±5D)	D85 (-3D)	D85 (±3D)	D86	D87	D92 (±3D)	D113 (±7D)	D141, D197, D253 (±14D)	D309 (±14D)
Visit Type	SRN	Pre IMP	IMP	CRU	TC	CRU	Pre IMP	IMP	CRU	TC	CRU	CRU	Pre IMP	IMP	CRU	TC	CRU	EoT CRU	CRU	EoS/ET CRU
Weight	X		X					X						X				X	X	X
Physical exam ^{4,8}	X		X					X						X				X		X
Neurological exam ^{4,8}	X		X					X						X				X		X
TriPLICATE ECGs ⁴	X		X			X		X			X			X				X	X	X
MRI ¹⁷	X																			
Laboratory Assessments ^{4,9}																				
HIV, HCV, HBV	X																			
Coagulation	X																			
Clinical chemistry ⁴	X	X				X	X				X	X	X					X	X	X
Hematology ⁴	X	X				X	X				X	X	X					X	X	X
Urinalysis ⁴	X	X				X						X						X		X
Urine drug screen ⁴	X	X				X						X								
Pre-IMP alcohol breath test ⁴	X		X					X									X			
Pre-IMP pregnancy test ^{4,11}	X		X					X									X			
FSH ¹¹	X																			
Inflammatory markers ^{4,12}	X	X				X						X						X		X
Cytokine panel (pre- and post- IMP) ¹³		X	X			X	X					X	X							
Pharmacodynamic Assessments ⁴																				
Serum antibodies ^{4,14}		X				X	X				X	X	X					X	X	X
Serum CGRP ⁴		X				X	X				X	X	X					X	X	X

Visit Number ¹	Screen ²	V1 ^{2,5}		V1a ⁵	V1b ⁵	V2	V3 ⁵		V3a ⁵	V3b ⁵	V4	V5	V6 ⁵		V6a ⁵	V6b ⁵	V7	V8	V9, V10, V11	V12/ET
Week	Up to 4 wks	W0				W1	W4				W5	W8	W12				W13	W16	W20, W28, W36	W44
Day (Visit Window)	-28 to -1	D1 (-3D)	D1 --	D2	D3	D8 ($\pm 3D$)	D29 (-3D)	D29 ($\pm 3D$)	D30	D31	D36 ($\pm 3D$)	D57 ($\pm 5D$)	D85 (-3D)	D85 ($\pm 3D$)	D86	D87	D92 ($\pm 3D$)	D113 ($\pm 7D$)	D141, D197, D253 ($\pm 14D$)	D309 ($\pm 14D$)
Visit Type	SRN	Pre IMP	IMP	CRU	TC	CRU	Pre IMP	IMP	CRU	TC	CRU	CRU	Pre IMP	IMP	CRU	TC	CRU	EoT CRU	CRU	EoS/ET CRU
PBMC for ELISpot ⁴		X																X		
Blood collection for research sample ^{4,15}		X				X	X				X	X	X				X	X	X	X
HLA typing (optional)																			X ¹⁹	X ¹⁹
Laser imaging and capsaicin challenge ⁴	X	X				X					X	X						X	X ¹⁶	X ¹⁶

Abbreviations: AE = adverse event; CRU = Clinical Research Unit; D = day; DBF = dermal blood flow; ECG = electrocardiogram; EoS = End of Study; EoT = End of Treatment; ET = Early Termination; FSH = follicle-stimulating hormone; H = hour; HBV = hepatitis B virus; HCV = hepatitis C virus; HIV = human immunodeficiency virus; IM = intramuscular; IMP = investigational medicinal product; LSCI = Laser Speckle Contrast Imaging; MRI = magnetic resonance imaging; PBMC = peripheral blood mononuclear cell; PD = pharmacodynamic; SAE = serious adverse event; SD = standard deviation; SRN = Screening; TC = telephone call; V = visit

1. The Investigator may perform visits outside of the scheduled study visits (unscheduled visits) listed in the table to conduct evaluations or assessments required to protect the well-being of the participant.
2. Screening and V1 visits can be rescheduled, and Screening window may be extended.
3. AEs/SAEs recording from time of informed consent up to and including Follow-up or ET.
4. On IMP administration days, all laboratory, PD, and capsaicin assessments are to be performed prior to IMP administration.
5. After each IMP administration, (a) participants will stay for 6 hours (± 2 hours) after injection for safety observation (except for sentinel participants who will stay for 24 hours after the first dose), (b) participants (except the sentinels' first dose) will have an approximately 24-hour onsite safety review including review of vital signs, temperature, diary, AEs, and medications, (c) all participants will have a telephone call approximately 48-hours post IMP injection for safety check including AE and medication review, and (d) all participants will complete a diary daily for 7 days, starting from the day of IMP administration.
6. On IMP administration days, vital signs (including temperature) will be measured before and after IMP administration.
7. Participants should be resting in a semi-recumbent position for at least 10 minutes before vital signs measurements. Semi-recumbent vital signs will include heart rate, systolic and diastolic blood pressure, respiratory rate, and body temperature.
8. Full neurological and physical examinations are to be performed during Screening, at Week 16 (EoT), Week 44 (EoS), and ET; brief (targeted) examinations may be performed at all other visits.
9. Laboratory assessments are detailed in Section 7.7 and Appendix 1.

10. A diary will be dispensed on Day 1. Participants will complete it for 7 days daily, starting on the day of each administration of IMP.
11. For females of childbearing potential only, blood pregnancy test at Screening and urine test at other visits. For females of nonchildbearing potential in post-menopausal state, FSH at screening.
12. Inflammatory measures in blood will include but are not limited to C-reactive protein and erythrocyte sedimentation rate. At Screening only, antinuclear antibody, IgM rheumatoid factor, and anti-cyclic citrullinated peptide.
13. Cytokine blood samples will be collected pre-dose and approximately 6 hours (± 2 hours) post-dose, and only analyzed at the Investigator's discretion if clinically indicated; otherwise, they will be analyzed at the EoT visit. The cytokine panel will include but is not limited to IFN- γ , IL-2, IL-4, IL-6, IL-8, and TNF- α .
14. Antibody measures in blood, including but not limited to anti-CGRP target epitope, anti-UBITh, anti-CpG1, and isotyping of anti-CGRP antibodies.
15. A sample to be obtained as allowed by local regulations and participant consent.
16. After Week 16, LSCI assessment may no longer be required once the average capsaicin-induced DBF increase within that cohort has returned to baseline (i.e., DBF response ± 2 SD before administration of IMP within a cohort).
17. Historic MRI within 90 days of Screening may be accepted.
18. IMP should be administered to the opposite arm that was used to take blood. Alternate arms should be used for injection visits and the arm used for IMP administration should be recorded.
19. A blood sample to be obtained for HLA typing at any post-Week 16 visit as allowed by participant consent. Blood sample is only to be collected at one visit.

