**Table 1. Objectives and Endpoints**

Objectives	Endpoints
Primary Safety and Tolerability	
To evaluate the safety and tolerability of UB-313, when administered at selected dose regimens given intramuscularly (IM) to healthy adults.	Safety will be assessed by adverse events (AEs), adverse events of special interest (AESIs), medically attended adverse events (MAAEs), local (injection site) and systemic (generalized) reactions (i.e., reactogenicity), clinical laboratory assessments (e.g., chemistry, hematology, urinalysis), vital signs, neurological and physical examinations and electrocardiograms (ECGs), through the end of study.
Primary Immunogenicity	
To evaluate the anti-Calcitonin Gene-Related Peptide (anti-CGRP) specific antibody responses to selected UB-313 dose regimens in healthy adults.	Immunogenicity will be measured serum anti-CGRP antibody titers and analyzed from baseline to Week 16 and Week 44.
Secondary	
To evaluate the effects of selected UB-313 dose regimens on capsaicin-induced dermal blood flow (DBF) as a surrogate marker of target engagement.	Pharmacodynamics (PD) of the immune response will be measured by the inhibition of capsaicin-induced increase in DBF and will be analyzed from baseline to Week 16 and until return to baseline or until Week 44, whichever comes first.
Exploratory	
To evaluate the effects of selected UB-313 dose regimens on CGRP concentrations in serum.	CGRP concentrations in serum through the end of study.
To characterize antibodies generated by UB-313.	Antibody titers against components of the UB-313 (i.e., CpG1 and UBITh1) through the end of study. Isotype-specific anti-CGRP antibody titers through the end of study.

To examine cytokine release induced by UB-313.	Cytokine release from peripheral blood mononuclear cell (PBMC)s stimulated with component of the UB-313 (T-cell ELISpot) through Week 16.
--	---

[figure not shown]

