**Figure 1 Study Design Schematic**

\*No more than 4 participants will be dosed in a 24-hour period.

\*No more than 4 participants will be dosed in a 24-hour period.

Abbreviations: C (capsaicin Challenge); EoS (End of Study); EoT (End of Treatment); M (month); SCR (Screening Period); h (hour); Wk (week).

SRC (Safety Review Committee) is responsible for the safety review and dose escalation decision. At the end of Week 16, an EoT analysis will be performed for each cohort, unblinded by treatment cohort and pooled by dose on all safety, tolerability, immunogenicity and DBF data. At the end of the treatment analysis, study team members who are responsible for the conduct and data management of the study, and participants will remain blinded to the subject level treatment assignment. If there are no safety concerns, the study will continue until all participants complete Week 44 (End of Study [EoS]) visit. An unblinded statistics team from an external CRO (AvanSight) will perform the EOT and EOS analyses.

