### **4.0 General Consideration**

All analyses will be conducted using observed data only and no missing data will be imputed.

In general, the baseline value is defined as the last available value before the first injection of study dose.

All analysis and summary will be performed by dose group, defined as below:

- 100/100/100 $\mu$ g (8 active participants in cohort 1)
- 300/100/100 $\mu$ g (8 active participants in cohort 2)

- 300/300/300 $\mu$ g (8 active participants in cohort 3)
- 600/100/100 $\mu$ g (8 active participants in cohort 4)
- Placebo (8 participants from all cohorts)

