#### **5.1.2.5 Duration of Inhibition Response (Exploratory)**

Duration of inhibition response is defined as from baseline to either return to baseline or until Week 44, whichever comes first for inhibition responders. Participants who do not return to baseline will be censored at the time of study exit.

Duration of inhibition response will be summarized for each dose group, using Kaplan-Meier product-limit estimates.

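### Duration of inhibition is censored at study exit, although LSCI may stop earlier for a whole cohort, so up to 196 unmeasured days count as event-free

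*Protocol*

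**What the plan says.** - **Stop rule, cohort level.** Protocol Table 1, footnote 16: "After Week 16, LSCI assessment may no longer be required once the average capsaicin-induced DBF increase within that cohort has returned to baseline". The synopsis (Capsaicin Challenge) gives the same rule with its limit, that the "average capsaicin induced DBF increase within that cohort has returned to baseline (i.e., DBF response ± 2 SD before administration of IMP" within a cohort. Stopping is permitted, not required.
- **Duration, participant level.** SAP 5.1.2.5 runs from baseline to return to baseline or Week 44, among inhibition responders, and uses Kaplan-Meier estimates by dose group. Its censoring rule is: "Participants who do not return to baseline will be censored at the time of study exit".
- **Study exit.** Under SAP Figure 1, absent safety concerns, "the study will continue until all participants complete Week 44 (End of Study [EoS]) visit".
- **Endpoint.** SAP Table 1 has the secondary PD endpoint "analyzed from baseline to Week 16 and until return to baseline or until Week 44, whichever comes first". Ending PD follow-up at a return to baseline is therefore planned.
- **Purpose.** Under Statistical Considerations, the protocol synopsis says that in the second phase "effects of the 4 dosage regimens of UB-313 on the duration of responses will be evaluated".
- **Groups.** SAP 4.0 makes each active dose group the 8 active participants of one cohort. The comparator is "Placebo (8 participants from all cohorts").

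SAP 5.1.2.1 lists the DBF visits after Week 16 with the qualifier that they apply where applicable. SAP 5.1.2.5 does not mention the cohort stop and gives no individual criterion for return.

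**The concern.** The two rules work at different levels. A cohort average can be back at baseline while some of its responders are not. Once LSCI stops, those responders cannot be seen to return, but the SAP keeps them in the risk set as still inhibited until they leave the study. Time without a measurement is then treated as time without an event. SAP 4.0 restricts analyses to observed data, and this rule does not fit that principle. At stake is how the duration curves read after a cohort's last LSCI, which is the period the second phase was set up to describe.

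**Working it through.** The plan states no figure of its own here, so the gap follows from its visit days.

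**1. Unmeasured time.** Inputs: LSCI days from SAP 5.1.2.1; Week 44 is Day 309 (44 × 7 + 1) and Week 16 is Day 113 (16 × 7 + 1). Gap = exit day − last LSCI day.

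| Last LSCI | Gap to Day 309 |
|---|---|
| Day 113 (Week 16) | 309 − 113 = 196 days |
| Day 141 (Week 20) | 309 − 141 = 168 days |
| Day 197 (Week 28) | 309 − 197 = 112 days |
| Day 253 (Week 36) | 309 − 253 = 56 days |

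Footnote 16 is attached to the LSCI entries from Week 20 onward, so Week 16 can be the last mandatory measurement. If the average must be seen to return after Week 16, the longest gap is 168 days. With the visit windows (±7 days at Week 16, ±14 at Week 44), the 196-day gap ranges from (309 − 14) − (113 + 7) = 175 to (309 + 14) − (113 − 7) = 217 days.

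**2. Active dose group.** Each Kaplan-Meier step multiplies the estimate by 1 − d/n, with d events among n at risk. If the cohort stops at one visit, d = 0 for the whole group from then on, under either censoring rule, so every step is the same. What differs is that exit censoring draws the curve flat to Day 309, keeps the unmeasured responders in the numbers at risk, and yields a Week 44 estimate with no data behind it. Censoring at the last LSCI ends the curve there.

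**3. Pooled placebo group.** Each cohort contributes 10 − 8 = 2 placebo participants, and cohorts can stop at different times. Suppose r placebo responders are still measured, m are unmeasured because their cohort stopped, and d return at a later visit. The step is:

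- censoring at last LSCI: 1 − d/r
- censoring at study exit: 1 − d/(r + m)

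For d > 0 and m > 0 the second is larger, so the estimated proportion still inhibited is too high. This needs at least one unreturned placebo responder in a stopped cohort and a later observed return in another.

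**4. Secondary note on the stop limit.** The supplied text does not say which SD is meant or whether placebo participants are averaged in. Let s be the active-arm shift below baseline, with placebo unchanged. The cohort-of-10 mean then shifts by (8s + 2 × 0)/10 = 0.8s.

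| Reading of SD | Active only | Placebo pooled |
|---|---|---|
| Between participants | s ≤ 2.0 SD | s ≤ 2/0.8 = 2.5 SD |
| SD of the mean | s ≤ 2/√8 = 0.71 SD | s ≤ (2/√10)/0.8 = 0.79 SD |

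**The case against.** The case for leaving the plan alone has four parts.

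- **The analysis is minor.** Duration of inhibition is exploratory, with 8 active participants per dose group, and the stop is optional. The primary immunogenicity endpoint and the DBF ANCOVA in SAP 5.1.2.1 do not use the censoring date. This stands and limits the weight of the point.
- **Moving the censoring date changes no step in an active group.** This also stands. It leaves the flat tail, the numbers at risk, the Week 44 estimate and the placebo group.
- **196 days is an extreme.** It requires a cohort average back at baseline at Week 16, 113 − 85 = 28 days after the third injection and at the time point the protocol uses for maximal response. Such a cohort would probably have few responders. This stands.
- **Stopping at return is planned.** It is, but an average that has returned does not show that each participant has, and SAP 5.1.2.5 needs the individual result.

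Stronger readings are tempting. A reader might infer that a cohort stopped early would look the longest-lasting. The documents do not support that: the height of the plateau depends on how many responders have already returned, and it may be low. A reader might also infer that the ±2 SD rule ends LSCI while inhibition clearly persists. That holds only for a between-participant SD, and full protocol sections not available here may define it otherwise. Nor do the documents show that LSCI must continue in every cohort or that a different stop limit is needed; those are trade-offs between burden and information.

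**Conclusion.** The censoring rule in SAP 5.1.2.5 is wrong as written whenever a cohort's LSCI stops before Week 44 with a responder not individually returned. It then counts a nominal 56 to 196 unmeasured days as event-free. This conclusion does not depend on which SD the stop rule uses, although the SD affects how often the situation would arise. It assumes that the optional stop is used, that completers exit at about Day 309 and, for the statement that no step changes, that a cohort stops at one visit. How many participants would be affected cannot be derived from the documents, which give neither the variability of DBF nor an individual return criterion.

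The ambiguity of the SD is a secondary matter for confirmation, not an established defect.

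**What to change.** In SAP 5.1.2.5:

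1. Censor responders who have not returned at their last evaluable LSCI assessment instead of at study exit.
2. Report no Kaplan-Meier estimate beyond a group's last LSCI assessment.
3. State the individual criterion for return to baseline: the measure, the post-capsaicin time point and the limit. The event cannot be derived without it.

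This takes a few sentences in the SAP and needs no new data or visits. The curves of stopped cohorts will end earlier. The change does not recover the unobserved return times; it only stops the analysis from implying that they are known.

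Separately, check the full protocol for which SD the stop limit uses and whether the 2 placebo participants per cohort enter the average. If it is defined there, repeat the definition in the synopsis and footnote 16; if not, add it.
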